Physical Therapy may include:

- Ultrasound
- Transcutaneous electrical nerve stimulation (TENS)
- Braces/Splints/Straps
- Extracorporeal Shockwave therapy
- Deep transverse frictions for tennis elbow
- Exercise therapy
- Stretching
- Eccentric exercises

Current treatments for pain have yielded mixed results. Pain relief and anti-inflammatory medications remain the primary treatment option of choice; however, only about half of patients who take prescription and/or over-the-counter medication for chronic pain reported ineffective pain relief. Additionally, prescription painkiller use abuse and addiction rates are very high and a major contributor to unintentional drug deaths.

STUDY DESIGN

A multi-center, triple-blind, placebo-controlled, randomized evaluation of the effect of the MR5® Prototype Device for temporary adjunctive use to relieve pain associated with Lateral Epicondylitis.

SUBJECT GROUPS

Each subject will be randomized to one of two test procedure as follows:

MR5® Prototype Device for temporary adjunctive use to relieve pain associated with Lateral Epicondylitis.

Test procedure groups:

- A. Subjects randomized to the test procedure group 1 will receive the study procedures with the active (true) Multi Radiance Medical® MR5® Prototype Device (light only).
- B. Subjects randomized to the control procedure group will receive the study procedures with a 'fake' (placebo) Multi Radiance Medical® MR5® Prototype Device.

The 'fake' (placebo) MR5 Prototype device will appear to the subject to be an active device but will not produce any therapeutic light output. The placebo laser device is designed to have the same physical appearance as the actual (active test) device, including the appearance of any **visible** light output. Therefore, both the test and control devices emit light when activated that is indistinguishable to the subject. As the laser light does not put out any notable degree of heat or noise, these are not distinguishing factors for subjects between the active and control devices.

Apart from the distinction of whether the subject receives the study procedures with the actual or the fake laser device, all subjects and investigative parties will adhere to all phases of the entire protocol design.

SUBJECTS

Recruitment

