This clinical study will be a triple-blind design, such that neither the subject, nor the assessor, nor the therapists will be aware of whether a subject is receiving the study procedure with the active (test procedure group assignment) or the 'fake' (placebo procedure group assignment) Multi Radiance Medical MR5 Prototype Device until after the study is completed.

Maintenance of study triple-blind throughout the entire course of the study will be achieved through the following means:

- Each subject will be randomly assigned to 'Test Group A' or 'B' by the independent study Monitor. Only the study Sponsor will know which label 'Test Group A' or 'B' corresponds to the actual (test) MR5 device and which label corresponds to the 'fake' device until the final study data analysis is complete. The Sponsor will ensure that this information is stored and maintained confidentially at the Sponsor's work site. This knowledge will not be shared with the investigators, the subjects, or the study Monitor until the final data analysis is complete.
- The fake (placebo) MR5 device is designed to have the same physical appearance as the actual MR5 device, including the appearance of any **visible** light output. Therefore, both the test and sham devices emit light when activated that is indistinguishable to both

the subject and to the investigator. As the laser light does not put out any notable degree of heat or noise, these are not distinguishing factors for subjects between the four groups.

3) There will be two independent investigators interacting with subjects at each test site:

- Administration investigator*: who will be responsible for administrating the study procedures; and
- Assessment investigator*: who will be responsible for recording the study outcome measures

Only the administration investigator will be aware of whether a subject is assigned to 'Test Group A' or 'B', although he or she will not be made aware of whether 'Test Group A' or 'B' corresponds to the true or fake laser. Neither the assessment investigator nor the subject will be aware of the subject's A/B Group assignment. In this way, the assessment investigator will not be able to form an association between A/B Procedure Group and active/sham device over the course of the study if a treatment effect is observed.

4) During the MR5 procedures, both the subject and the administration investigator will wear Laser Safety Industries protective eyewear that filter out the laser light spectrum.

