PERCEIVED GROUP ASSIGNMENT: The subject, the Administration Investigator and the Assessment Investigator will each be asked (separately) to state whether he or she believes the subject to have received the active procedure administrations with the actual Multi Radiance Medical® MR5® Prototype Device or the ‘fake’ procedures with the ‘placebo’ MR5® device, and the reasons for those beliefs.

STUDY PROCEDURE PROTOCOLS

All study procedure protocol activities listed below will be conducted by a licensed health care provider at the test site. The study licensed health care provider will be a suitably qualified and licensed medical/healthcare professional who is trained and experienced in treating individuals with Lateral Epicondylitis, in evaluating according to the study qualification parameters, in recording the study outcome measures such as range of motion and medication history, and in performing adverse events evaluations.

PRE-PROCEDURE ACTIVITIES

The pre-procedure activities will be conducted at the test site prior to commencement of the study procedure administration.

STUDY QUALIFICATION

ATTAINMENT OF INFORMED CONSENT PROCESS

Informed consent is an agreement between the individual investigator (a licensed medical/healthcare professional) and each individual subject, having the capacity to understand and to make an informed decision. Informed consent is a process that is initiated prior to the potential subject agreeing to be considered for participation in the study and continues throughout the duration of the individual's study participation.

A written consent form describing in detail the purpose of the study, the study intervention, the study procedures, and the risks involved in taking part in the study is given to and reviewed with each subject, with voluntarily signed and dated documented informed consent required from the subject *prior to* starting any study subject activity, including study qualification evaluation. No other consent documents will be provided to subjects in this study. The consent form will be IEC-approved with supporting documentation.

The informed consent process will occur in a private room and be between the investigator and the subject.

The step-by-step processing for attainment of informed consent will be as follows:

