 - In performing these evaluations, the numerical design and analysis of the blinding assessment will follow that outlined in Bang, et al. (Bang H, Ni L, Davis CE, Assessment of blinding in clinical trials. *Control Clin Trials*. 2004; 25:143-56)
- (v) **Qualitative analysis confirmation:** Evaluation of the comments provided by the subject, administration investigators and assessment investigators in the rationale section to explain the guess at group alignment will be evaluated and interpreted as follows to either support or negate the numerical findings:
 - *Positive blinding efficacy* will be supported through qualitative assessment of comments provided to support perceived group assignment that pertain to the determination being made based on treatment efficacy or lack thereof; e.g.: 'I can move my head from side to side easily and without it hurting and I couldn't do that before, so I believe I got the real treatment' or 'I haven't noticed any change in my Lateral Epicondyle pain, so I believe I got the fake treatment.'
 - *Blinding will be determined to have failed* if comments provided to support perceived group assignment pertain to factors such as sensation/visual clues, such as 'I saw/didn't see a light go on', or other factors that pertain to blinding having been compromised such as 'I overheard the doctor saying I wasn't getting the real treatment.'

Sample stratification distribution plan

Sample Stratification

In order to account for the possibility that skin phototype could affect the absorption of the energy emitted from the study device, and to ensure that the study sample is representative of the range of skin phototypes in the intended U.S. clinical patient population, recruitment and enrollment of the final 50 study subjects will be further stratified by Fitzpatrick skin type, as determined according to race, according to the process of proportionate allocation using a sampling fraction in each of the strata that is proportional to that of the total sample population.

According to the United States Census Bureau (www.census.gov), the distribution of race throughout the United States population as of 2014 is as follows:

- White (not Hispanic/Latino): 62%
- Hispanic/Latino: 17%
- African American: 13%
- Asian: 5%
- Other (including Hawaiian/Pacific Islander, America Indian, Alaskan and 2+ races): 3%

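### The rule that declares blinding failed on visual or sensation comments ignores correctness, arm and count, so it can return a failure verdict when clue-based guesses were no better than chance

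*Combined protocol and SAP*

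**What the plan says.** All references are to the combined protocol and SAP.

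- **Perceived Group Assignment.** The subject, the administration investigator and the assessment investigator each state separately which device they think was used, "and the reasons for those beliefs". This is done within 24 hours of the sixth procedure and again at the one-month visit.
- **Blinding Efficacy Evaluation, items (i) to (iv).** Correct and incorrect guesses are reported for each type of rater, compared within and between groups, and analysed by a published blinding method. No cut-off for failure is given.
- **Item (v), qualitative confirmation.** The comments are "interpreted as follows to either support or negate the numerical findings". Remarks about benefit or lack of it count in favour of blinding. On the other side, "Blinding will be determined to have failed" "if comments provided to support perceived group assignment pertain to factors such as sensation/visual clues". The example is "I saw/didn't see a light go on". Overhearing staff disclose the allocation is a further trigger.
- **Subject Groups.** "both the test and control devices emit light when activated that is indistinguishable to the subject".
- **Triple Blind Design.** "both the test and sham devices emit light when activated that is indistinguishable to both" subject and investigator. During procedures, "both the subject and the administration investigator will wear Laser Safety Industries protective eyewear that filter out the laser light spectrum".

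**The concern.** A blind is broken by a clue when the clue tells people which arm they are in. That requires the clue to go with correct guesses or to differ between arms. Item (v) tests neither. It looks only at the topic of the comment, and its example counts both seeing and not seeing a light as failure.

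The sham is meant to look lit, and the eyewear is meant to filter the light. Both kinds of comment are therefore foreseeable in both arms under the blinding measures the protocol itself adopts.

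At stake is the credibility of the blinding report. The primary outcome is a self-rated pain score, and the results are intended to support a De Novo submission. A prespecified statement that blinding failed, standing above a numerical index that shows no such thing, would be hard to explain afterwards.

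**Working it through.** The blinding section states no threshold, count or error rate, so there is no figure of the plan to reproduce. The check is mainly textual, with two illustrations.

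**1. The rule against the device design**

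| Comment and guess | Arm | Guess | What it says about the blind | Item (v) |
|---|---|---|---|---|
| Saw a light, so active | Placebo | Wrong | The light did not reveal the allocation | Failure |
| Saw no light, so placebo | Active | Wrong | The clue misled the subject | Failure |
| Saw a light, so active | Active | Right | Uninformative if placebo subjects say the same | Failure |
| Saw no light, so placebo | Placebo | Right | A warning if such comments cluster in this arm | Failure |

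Only the last row, or a pattern across rows, points to a broken blind. Item (v) treats all four alike.

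**2. A constructed case**

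Take the plan's target of 25 evaluable subjects per group. Suppose everyone sees the light and guesses active. The per-arm index is (correct − incorrect)/n.

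- Active: (25 − 0)/25 = +1.
- Placebo: (0 − 25)/25 = −1.
- Correct overall: 25/50 = 50%.

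The light did not separate the arms, yet item (v) declares failure.

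**3. How easily the rule could be triggered (illustration only)**

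Inputs from the documents: 60 subjects (Sample size), 3 raters (Perceived Group Assignment) and 2 time points. That gives 60 × 2 = 120 subject comments, or 60 × 3 × 2 = 360 comments in all.

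Assumptions not in the documents:

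- A share q of comments mentions a light or sensation although the sham works.
- Comments are independent.
- The rate is the same for all raters.
- Nobody is lost.

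The text does not say whether one comment is enough, so two readings are shown.

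- At least one: 1 − (1 − q)^m
- At least two: 1 − (1 − q)^m − mq(1 − q)^(m−1)

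| q | m = 120, ≥1 | m = 120, ≥2 | m = 360, ≥1 | m = 360, ≥2 |
|---|---|---|---|---|
| 0.5% | 45% | 12% | 84% | 54% |
| 1% | 70% | 34% | 97% | 88% |
| 2% | 91% | 69% | 99.9% | 99% |

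With the 50 subjects the plan expects to retain, the at-least-one figures at q = 1% become 1 − 0.99^100 = 63% and 1 − 0.99^300 = 95%.

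The range, from 12% to nearly 100%, shows how much depends on an unknown rate and an unstated trigger. It does not estimate the risk.

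**4. What a few comments can show**

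If 5 of 5 sensory guesses are correct, the exact two-sided 95% lower limit is 0.025^(1/5) = 47.8%. Five or fewer such comments can therefore never exclude chance (50%). A replacement rule that relied on the interval alone would be unable to detect a real leak from so few comments.

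**The case against.** Four objections carry weight.

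- **Correctness is counted elsewhere.** A reader might infer that the plan ignores whether guesses were right. It does not: items (i) to (iv) count correct guesses, and those results would stand beside any qualitative verdict. The criticism applies to item (v) alone. It survives because item (v) may negate the other items and they set no cut-off.
- **Failure is not inevitable.** A reader might infer that the rule always fails a working sham. Someone must first make such a comment, and the text speaks of comments in the plural without fixing a number. The percentages also assume equal rates across raters, although the assessment investigator only records outcomes, and independence, although the same people are asked twice.
- **The sham's success is not a given.** Indistinguishable light is a design intention, and this evaluation exists to test it. A single placebo subject who saw a light does not show that the sham worked. A report of no light could flag a device that was not emitting, though the eyewear makes that ambiguous. Asking about light is therefore sensible, and the prompt should stay.
- **Nothing gates on the verdict.** A reader might infer that a failure verdict would invalidate the placebo comparison. No section ties it to the primary analysis, the analysis set or the success criteria.

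The disclosure trigger is a genuine sign of unblinding and is not in dispute.

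**Conclusion.** The concern holds for item (v). The section's only explicit failure criterion, with power to set aside the numerical results, depends on the subject matter of comments and not on whether they reveal allocation. Given the device design and the eyewear, it can declare failure when clue-based guesses were no better than chance. This is a faulty decision rule, not merely missing detail.

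The size cannot be fixed from the documents. The frequency of such comments is unknown, and the number needed is not stated. The effect is limited to the blinding report; the primary test does not change. The conclusion rests on the protocol's own description of the two devices and the eyewear, not on any assumed comment rate.

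**What to change.** Replace the automatic failure verdict in item (v) as follows.

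1. Before the A/B key is broken, code each stated reason as efficacy, sensory/visual, disclosure or other. Keep comments about light as a coded category, not as an automatic sign of failure.
2. Tabulate the codes by rater type, arm and correct or incorrect guess, with counts and exact confidence intervals, beside the blinding index.
3. Treat sensory/visual comments as evidence of a broken blind only where they go with correct guesses or differ between arms.
4. State that a wide interval from few comments proves neither success nor failure of blinding.
5. List confirmed disclosures individually, with a sensitivity analysis that excludes those subjects.

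The guesses and reasons are already collected, and the sponsor already withholds the A/B key until the final analysis is complete, so blind coding needs no new procedure. The cost is a change of SAP wording, a small coding table and minor analyst time. The drawback is that few comments may leave the question inconclusive, and the report should then say so.

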- Overall study success criteria of at least a 30% difference between the test device group and the placebo group, comparing the proportion of individual successes in each group.
- It is anticipated that about 50% of subjects in the test device group and about 20% of subjects in the placebo group will meet the individual success criteria, and
- Intended application of a two-tailed test with an alpha value of 0.05 and Power of 0.8

- the sample size of 25 available subjects per group (test group and the control group, separately) has been determined using the following reference calculator: *Hypothesis Testing: Categorical Data - Estimation of Sample Size and Power for Comparing Two Binomial Proportions* in Bernard Rosner's *Fundamentals of Biostatistics*.

For the purposes of sample size calculation, a subject loss-to-follow-up of 20% is anticipated.

Therefore, a minimum starting sample size of 30 evaluable subjects in each group is needed to ensure that a sufficient number remains at the end of the trial (25 subjects per group) for any significant differences found between groups to be considered statistically valid and representative of the general population being sampled. This results in a total of 60 subjects being enrolled in this study across both study procedure groups.

RANDOMIZATION

Subject allocation to procedure group will be via variable block randomization with varying block sizes of two and four used at random to minimize the likelihood of predicting the next procedure group assignment. In addition, randomization will be stratified by Fitzpatrick Skin Type grouping

Randomization will be attained using computer generation sequence methodology, ensuring that the randomization methodology and the generated allocation sequence is concealed from the investigator and subjects.

Concealment will be insured as follows:

- Each computer-generated randomization sequence is unique and will therefore not be able to be replicated.
- Randomization will occur to either 'Test Group A' or 'B' rather than to a tests or placebo group, and only the study Sponsor will know which assignment corresponds to the active devices and which corresponds to the fake device. The Sponsor will not reveal this information to any source (investigators, subjects, or study Monitor) until the final study data analysis is complete.

TRIPLE BLIND DESIGN

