The pre-procedure assessment phase will commence following successful completion of the individualized pain management regimen stabilization phase and just prior to commencement of the procedure administration phase.

CONTINUED STUDY ELIGIBILITY EVALUATION

Prior to the subject commencing the Pre-Procedure Assessment phase of the study, the investigator will:

- review the subject's recordings of use/application of his or her individualized pain management regimen to ensure it was correctly applied and recorded, and that there are no deviations significant enough to warrant withdrawal of the subject from the study prior to entry to the pre-procedure assessment phase; and
- calculate the average of the 3 VAS degree of pain scores recorded during the last three days of the individualized pain management regimen stabilization phase. In order for the subject to proceed, the 3-day average VAS score must be 50 or greater. If it is less than 50, the subject's participation in the study ends at this time.

PRE-PROCEDURE MEASURES

- Degree of Pain Rating. This will occur within 15 minutes prior to the initial procedure administration. The exact time the VAS rating is recorded will be noted.
- PRTEE, Grip Strength and TNFa measurements will be noted.

PRE-PROCEDURE VARIABLES

- Baseline concomitant medication and treatment/therapy use
- Historical pain medication and treatment/therapy use
- Baseline Lateral Epicondyle pain variables
- PRTEE, Grip Strength and TNFa measurements and Fitzpatrick Skin Type Classification will be noted.
- Demographics

PROCEDURE ADMINISTRATION PHASE

PROCEDURE ADMINISTRATION PROTOCOL

- The procedure administration phase of the study will commence within 15 minutes subsequent to completion of the pre-procedure assessment phase.
- The procedure administration phase comprises a total of six procedure administrations with the Multi Radiance Medical® MR5® Prototype Device: two

procedures a week for three consecutive weeks*, each procedure administration three to four days apart.

[figure not shown]
- *Three weeks, 2 times a week... Follow-up at 4th week after administration phase*

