Applying stratification according to the process of proportionate allocation using a sampling fraction in each of the strata that is proportional to that of the total sample population, the following formula is applied:

$$X = x1*X + x2*X + x3*X + x4*X + x5*X; \text{ where}$$

- X = Total Sample Population = 50 subjects
- x1 = Subpopulation: White = 0.62; $0.62*50 = 31$ subjects
- x2 = Subpopulation: Hispanic/Latino = 0.17; $0.17*50 = 8.5$ subjects
- x3 = Subpopulation: African American = 0.13; $0.13*50 = 6.5$ subjects
- x4 = Subpopulation: Asian = 0.05; $0.05*50 = 2.5$ subjects
- x5 = Subpopulation: Other = 0.03; $0.03*50 = 1.5$ subjects

Furthermore, in the following reference ...

Sauer's Manual of Skin Disease; Brian J Hall, John C. Hall; 2012

Chapter 35: Skin Disease in Ethnic Skin; [name] & [name] ... Fitzpatrick Skin Type is associated with race, as follows:

- "White": (Not Hispanic/Latino): Fitzpatrick Skin Types I, II & III
- "Ethnic" (Hispanic/Latino; African American, Asian): Fitzpatrick Skin Types IV, V & VI

In consideration of the distribution of race in the U.S population as determined above, this results in the need to recruit:

Ø 31 subjects with Fitzpatrick Skin Type I, II or III

Ø 19 subjects with Fitzpatrick Skin Type IV, V or VI (17 Hispanic/Latino+13 African American+5 Asian+3 'Other')

For ease and uniformity of randomization, given that there will be three test sites, and two procedure administration groups the sampling plan is rounded to even numbers within individual groups, as follows:

Test Site #1		
	Skin Type I, II & III	Skin Type IV, V & VI
Test Group	7	5
Placebo Group	8	4

Test Site #2		
	Skin Type I, II & III	Skin Type IV, V & VI
Test Group	4	3
Placebo Group	4	3

Test Site #3		
	Skin Type I, II & III	Skin Type IV, V & VI
Test Group	4	2
Placebo Group	4	2

While every effort will be made to recruit subjects evenly across the range of Fitzpatrick Skin Types within each of the two categories, it is anticipated that the majority of recruited Skin Types will fall within the range of II to V, inclusive, proportionate within the respective categories, as Fitzpatrick Skin Types I and VI are the least predominant Skin Types amongst the U.S. population.

Once a Fitzpatrick Skin Type category has been filled at a test site, no additional subjects will be enrolled in that category at that site.

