FITZPATRICK SKIN TYPE CLASSIFICATION SCALE: The Fitzpatrick Skin Type Classification Scale is a numerical classification schema for human skin color developed in 1975 by Harvard Medical School dermatologist, [name], PhD. The scale classifies a person's complexion and their tolerance of sunlight.

The Fitzpatrick Classification Scale classifies skin type from I through VI according to the applicable criteria contained in the chart below.

Skin Type	Skin Color	Characteristics
I	White; very fair; red or blond hair; blue eyes; freckles	Always burns, never tans
II	White; fair; red or blond hair; blue, hazel, or green eyes	Usually burns, tans with difficulty
III	Cream white; fair with any eye or hair color; very common	Sometimes mild burn, gradually tans
IV	Brown; typical Mediterranean Caucasian skin	Rarely burns, tans with ease
V	Dark Brown; mid-eastern skin types	Very rarely burns, tans very easily
VI	Black	Never burns, tans very easily

POOLABILITY EVALUATION

The primary efficacy outcome is a binary variable, with success defined as a 30% or greater reduction in self-reported Degree of Pain rating on the 0-100 VAS from baseline to study endpoint evaluation. Poolability analysis for this primary binary outcome will be via the Breslow-Day test for homogeneity of odds ratios.

Furthermore, poolability analysis will also be conducted for the continuous outcome of mean change from baseline to study endpoint in self-reported Degree of Pain ratings on the 0-100 VAS through a treatment-by-subgroup interaction term applying a logistic regression model that also includes the main effect terms of all treatment groups.

SAFETY ANALYSES

Safety analyses will be based on all subjects who were randomized to the test or to the placebo procedure group. Safety will be assessed by evaluating and comparing frequency and incidence of observed and/or reported adverse events between test and placebo procedure groups. A chi-square test with a continuity correction will be performed to compare the percentage of subjects who had adverse events between test and placebo group subjects.

CASE REPORT FORMS

The case report forms that will be used to collect the data from each subject in this clinical study can be found in **Appendix E**.

REFERENCES

ⁱ Bocock MG, Collier JM, McNair PJ, Simmonds M, Larmer PJ, Armstrong B. A framework for the classification and diagnosis of work-related upper extremity conditions: systematic review. *Semin Arthritis Rheum*. 2009;38:296-311.

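### Skin-type strata are assigned by race, which conflicts with the plan's own Fitzpatrick chart; the rating is scheduled only after randomization, and the role of site in the lists is unclear

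*Combined protocol and SAP*

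**What the plan says.** The sample stratification distribution plan gives its reason for stratifying: "In order to account for the possibility that skin phototype could affect the absorption of the energy emitted from the study device". A second aim is to represent the US range of phototypes. It then states the rule: "recruitment and enrollment of the final 50 study subjects will be further stratified by Fitzpatrick skin type, as determined according to race".

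The quota sizes come from US census shares, starting with "White (not Hispanic/Latino): 62" percent. A cited manual supplies the link to skin type. White is "Not Hispanic/Latino): Fitzpatrick Skin Types I, II & III", and Hispanic/Latino, African American and Asian are types IV-VI. The targets are 31 subjects of types I-III and 19 of types IV-VI. They are spread over a table of site by skin-type group by arm, introduced with the words "given that there will be three test sites, and two procedure administration groups". A skin-type category closes at a site once it is full.

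The classification chart comes directly after this. It works from skin colour and sun reaction, and its entry for type IV is "Brown; typical Mediterranean Caucasian skin".

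Four other places bear on the point:

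- The Randomization section says "randomization will be stratified by Fitzpatrick Skin Type grouping". It mentions neither race nor site.
- The table of subject events and the subject group randomization paragraph both put randomization before the stabilization phase.
- The pre-procedure variables, collected after stabilization, include the line "PRTEE, Grip Strength and TNFa measurements and Fitzpatrick Skin Type Classification will be noted".
- The covariate list in the primary efficacy methods includes Fitzpatrick type, to be adjusted for as applicable.

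**The concern.** The reason for stratifying concerns absorption of light by skin. Race is a proxy for that, and the plan's own chart shows where the proxy fails. A White subject with Mediterranean skin is in the I-III stratum by the race mapping and in type IV by the chart. The mapping also sends every subject counted as Hispanic/Latino to IV-VI whatever the skin. The 3% classed as Other are counted in the 19 although the mapping does not mention them. The mapping rests on US categories, whereas the inclusion criteria require fluency in Portuguese, so its fit to the recruited subjects is unknown.

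Timing adds to this. A stratum and a cap both need a grouping before randomization, but the only scheduled rating comes afterwards. If race supplies the grouping and the chart supplies the covariate, the same subject can carry two different skin types in one trial. What is at stake is balance of the arms on actual phototype, and agreement between strata, quotas and analysis.

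Site raises a separate question. A list stratified by skin type alone does not secure the per-site arm counts in the table.

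**Working it through.** **1. The plan's own figures reproduce.** Types I-III: 0.62 × 50 = 31. Types IV-VI: (0.17 + 0.13 + 0.05 + 0.03) × 50 = 8.5 + 6.5 + 2.5 + 1.5 = 19. In the site table, types I-III sum to 15 test + 16 placebo = 31 and types IV-VI to 10 + 9 = 19, with 25 per arm. The sites hold 24, 14 and 12 subjects.

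**2. Order of events.** Qualification, then randomization, then stabilization, then pre-procedure assessment with the Fitzpatrick entry. No skin-type rating appears among the qualification items. The only basis for grouping that the text supplies before randomization is race.

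**3. Subjects in the wrong stratum.** The documents give no race-by-type error rate, so the rate is an assumption. Let a share e of the 31 White subjects rate as type IV, with no error among the other 19.

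- Expected number misplaced = 31e, which is 3.1, 6.2 and 9.3 for e = 0.10, 0.20 and 0.30.
- Share of the variance of the true grouping left within the race strata = [31e(1−e)/50] / [p(1−p)], with p = (31e + 19)/50. For e = 0.10, p = 0.442 and the share is 0.0558/0.2466 = 0.23. For e = 0.20 it is 0.0992/0.2500 = 0.40. For e = 0.30 it is 0.1302/0.2456 = 0.53.
- Simulated chance that the arms differ by 4 or more in the true number of type IV-VI subjects (random blocks of 2 and 4 within race strata of 31 and 19): about 7%, 15% and 20%. It is 0% if the strata use the rated type.

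If the error runs in both directions at the same rate, the results are:

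| Error rate (assumed) | Misplaced, of 50 | Variance share not controlled | SD of arm difference in IV-VI count |
|---|---|---|---|
| 0% | 0 | 0% | 1.0 |
| 5% | 2.5 | 20% | 1.8 |
| 10% | 5 | 37% | 2.3 |
| 20% | 10 | 65% | 3.0 |
| 30% | 15 | 85% | 3.3 |

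Blocking with no stratification gives an SD of about 3.5. Race strata therefore keep part of the control in every row and lose nearly all of it only at high error rates.

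**4. Site balance.** Suppose one central list, with sites enrolling in mixed order. With 50 subjects, 25 per arm, the number on test at a site of size n is hypergeometric. P(arm difference of 4 or more) = 0.396, 0.345 and 0.321 for n = 24, 14 and 12. Simulating the stated blocks within skin-type strata gives much the same, about 41%, 35% and 32%.

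The result depends on how enrolment runs. If the sites enrol one after another, the chances are about 0%, 12% and 13%. With separate lists by site and skin-type group they are under 1% at each site.

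**The case against.** **Race may only size the quotas.** On this reading the census shares give 31/19 and the chart classifies each subject. The table cells are labelled by skin type, the plan wants recruitment spread across the individual types within each group (which race cannot determine), and the Randomization section does not mention race. This reading is possible. However, the stratification plan says outright that type is determined according to race, and nothing in the text schedules the earlier rating that the reading needs.

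**A late entry does not prove a late first rating.** The same pre-procedure list includes demographics and medication history, parts of which are already checked at qualification. The case report forms are not in the text available, so an earlier entry cannot be excluded. This stands: the timing is an inference from the schedule, not a stated fact.

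**A reader might infer that the strata do not control phototype at all, or that the trial's inference is compromised.** The documents do not support either. The plan's own mapping associates race with type, so control is partial. Randomization is valid whatever the stratifier. The primary Fisher's exact test uses neither skin type nor site, and a stable trait noted before the first procedure is a legitimate covariate. That adjustment is optional and does not enter the Fisher's test, which the plan justifies by assuming important covariates are balanced.

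**A reader might also infer that the per-site arm counts will not be met.** That assumes one central list with mixed enrolment. The site table can equally be read as the detailed plan and the Randomization section as its summary. Even an imbalance of 14 v 10 keeps 4 × 14 × 10 / 24² = 97% of the efficiency of an even split at that site.

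**Conclusion.** The conflict between the race mapping and the chart is in the text, and so is the mismatch between when a skin-type grouping is needed and when it is scheduled to be recorded. Followed as written, stratification controls phototype imperfectly and allows strata, caps and covariate to disagree for the same subject. The size, 3 to 9 of 50 in the wrong stratum, rests wholly on an assumed 10-30% of White subjects rating as type IV.

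The site issue is an inconsistency to settle. The chance of an arm difference of 4 or more at a site runs from under 1% to about 40%, depending on how the lists are built and how the sites enrol.

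Neither issue affects the validity of the randomization or of the primary test. The change is worth making because it replaces a stated rule with a better one at very little cost.

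**What to change.** - Rate every subject with the Fitzpatrick chart at qualification, before randomization, and record the rating there.
- Use that rating for the randomization stratum, the category caps and the covariate.
- Keep the race shares only to size the 31/19 targets, and delete the statement that an individual's type is determined by race.
- State in the Randomization section that lists are generated by site and skin-type group (I-III v IV-VI), in line with the site table.

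The cost is one short rating moved to an earlier visit and six small strata in list generation, of 15, 9, 8, 6, 8 and 4 subjects. No extra staff or procedure is needed, and the 31/19 targets do not change.
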